## 16.1. ANALYSIS OF IMMUNOGENICITY ENDPOINTS

Individual titre values for each endpoint, seroresponse and fold rise compared to baseline will be presented in a data listing.

### **16.1.1. QUANTIFICATION OF ANTIBODY LEVELS**

SARS-CoV-2 S, RBD and nucleocapsid antibodies will be assessed quantitatively using a validated multiplexed MSD immunoassay at each scheduled visit as per protocol section 1.3. SARS-CoV-2 NAb will be measured using validated pseudoneutralization assays.

The antibody titre measurements will be summarized at each scheduled visit using geometric mean titre (GMT) and geometric mean fold rise (GMFR).

Descriptive statistics for GMTs and GMFRs will include number of participants, GMT, 95% confidence interval (CI), median, minimum and maximum.

The ratio of post-treatment GMTs values between each immunocompromised cohort and immunocompetent group will be presented with corresponding 95% confidence limits.

The GMT will be calculated as the antilogarithm of  $\Sigma$  (base 2 log transformed titre/n), i.e. as the antilogarithm transformation of the mean of the log-transformed titre, where n is the number of participants with titre information. The 95% CI will be calculated as the anti-logarithm transformation of the upper and lower limits for a two-sided CI for the mean of the log-transformed titres.

The fold rise is calculated as the ratio of the post-vaccination titre level to the pre-vaccination titre level, i.e., the baseline level (See [Section 6.2](#)). GMFR will be calculated as anti-logarithm of  $\Sigma$  (base 2 log transformed (post-vaccination titre/ pre-vaccination titre)/n). The 95% CIs for GMFR will be calculated similarly to those for GMT.

The antibody titre measurements will be presented in a data listing.

#### **16.1.1.1. SUBGROUP ANALYSIS FOR QUANTIFICATION OF ANTIBODY LEVELS**

The analysis of quantification of antibody levels will be repeated for the subgroups defined in [Section 7.6](#).

#### **16.1.2. SERORESPONSE RATE**

Seroresponse is a binary outcome where a success is when the fold rise in titres compared to baseline is  $\geq 4$ .

Seroresponse will be calculated for the immunocompromised cohort (including the pooled immunocompromised cohort) and immunocompetent cohort and will be summarized at each scheduled visit as per protocol section 1.3.

The number and percentage of participants with post-vaccination seroresponse, and 95% CIs will be provided and the 95% CI of seroresponse rate will be calculated using the Clopper-Pearson exact method. For 0% or 100% seroresponse, a 97.5% CI will be provided.

The difference in the seroresponse rate between each of the immunocompromised cohort and immunocompetent patients will be presented with corresponding 95% confidence limits using the Newcombe score without continuity correction.

#### **16.1.3. SUBGROUP ANALYSIS FOR SERORESPONSE RATE**

The analysis of seroresponse will be repeated for the subgroups defined in [Section 7.6](#).

#### **16.1.4. CELL-MEDIATED IMMUNE RESPONSE**

CMI responses (i.e., B-cell and T-cell responses) will be assessed as per the schedule of events (refer to protocol, Section 1.3).

CMI data will be reported separately from the CSR.

#### **16.1.5. MISSING DATA IMPUTATION METHOD FOR IMMUNOGENICITY ENDPOINTS**

A titre value measured below the lower limit of quantification (LLoQ) will be imputed to a value that is half of the LLoQ in summaries and analyses, but will be listed as reported in the raw serology data. For example, a serologic assay with LLoQ = 30 generally reports values below LLoQ as “<30”. The data listings will present the values as “<30”, while values of 15 (i.e., 30/2) are to be used in the summaries and analyses.

Titre values measured as above upper limit of quantification (ULoQ) will be imputed at the ULoQ value.

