Sensitivity analysis- The immunogenicity of a 3-dose primary vaccination with AZD1222 with a 4-week dosing interval in SARS-CoV-2 naïve immunocompromised adults $\geq 18$ years.	SARS-CoV-2 naïve immunocompromised adults $\geq 18$ years, who don't have exclusionary important protocol deviations (IPDs) and received at 3 IM doses of AZD1222.	3 IM doses of AZD1222 with a 4-week dosing interval	A binary response, whereby participants who have a post-treatment seroresponse ( $\geq 4$ -fold rise in titres from visit 8 [pre-dose 3] to 28 days post third dose) as measured by the S and Neutralizing antibodies	For participants who withdraw from the study, did not receive 3 IM doses of AZD1222, or who use restricted medications judged to have the potential to interfere with the generation or interpretation of an immune response, absence of data following these participants' withdrawal or subsequent data following the IPDs will be treated as missing.  Participants who tested positive for SARS-CoV-2 infection (RT-PCR) will be censored at the date of the positive test.	Number and percentage of participants achieving a seroresponse ( $\geq 4$ -fold rise in titres from visit 8 value [pre-dose 3] to 28 days post third dose) as measured by the S and Neutralizing antibodies
The immunogenicity of	SARS-CoV-2 naïve immunocompromised	3 IM doses of AZD1222	a) SARS-CoV-2 specific GMTs in SARS-CoV-2 S and Neutralizing	For participants who withdraw from the study, did not receive	a) Ratio of post-treatment GMTs from day of baseline value to 28

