To describe the immunogenicity of the AZD1222 vaccination between 28 days post 3rd-dose compared to 28 days post 2nd-dose, in adults $\geq$ 18 years between SARS-CoV-2 naïve immunocompromised and immunocompetent participants.	SARS-CoV-2 naïve immunocompromised adults and immunocompetent adults $\geq$ 18 years, who don't have exclusionary important protocol deviations (IPDs) and received at least one IM dose of AZD1222.	3 IM doses of AZD1222 with a 4-week dosing interval	a) Ratio of SARS-CoV-2 specific GMT titres  b) Difference in seroresponse rates of SARS-CoV-2 specific titres ( $\geq$ 4-fold increase in titres from 28 days post dose 2 to 28 days post dose 3)	For participants who withdraw from the study, did not receive 3 IM doses of AZD1222, or who use restricted medications judged to have the potential to interfere with the generation or interpretation of an immune response, absence of data following these participants' withdrawal or subsequent data following the IPDs will be treated as missing.  Participants who tested positive for SARS-CoV-2 infection (RT-PCR) will be censored at	a) Ratio of post-treatment GMTs from 28 days post second dose to 28 days post third dose in SARS-CoV-2 S and Neutralizing antibodies for each SARS-CoV-2 naïve immunocompromised cohort (including the pooled immunocompromised cohort) and the immunocompetent participants  b) Difference in percentages of participants who have a post-treatment seroresponse ( $\geq$ 4-fold rise in titres from 28 days post second dose to 28 days post third dose) as measured by the S and

				the date of the positive test.	Neutralizing antibodies for each SARS-CoV-2 naïve immunocompromised cohort (including the pooled immunocompromised cohort) and the immunocompetent participants

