- Difference in proportion of participants who have a post-treatment seroresponse ( $\geq 4$ -fold rise in titres from day of dosing baseline value to 28 days post third dose [second dose for immunocompetent participants]) to the S antibodies between each immunocompromised cohort (including the pooled immunocompromised cohort) and immunocompetent participants.
- Ratio of post-treatment GMTs at 28 days post third dose in SARS-CoV-2 neutralizing antibodies (pseudo-neutralization assay) between each immunocompromised cohort (including the pooled immunocompromised cohort) and post-treatment GMTs at 28 days post second dose in SARS-CoV-2 neutralizing antibodies (pseudo-neutralization assay) in immunocompetent participants.
- Difference in proportion of participants who have a post-treatment seroresponse ( $\geq 4$ -fold rise in titres from day of dosing baseline value to 28 days post third dose [second dose for immunocompetent participants]) as measured by SARS-CoV-2 neutralizing antibodies (pseudo-neutralization assay) between each immunocompromised cohort (including the pooled immunocompromised cohort) and immunocompetent participants.

The supportive analysis to immunogenicity secondary endpoints are:

- Proportion of participants who have a post-treatment seroresponse ( $\geq 4$ -fold rise in titres from day of dosing visit 8 (pre-dose 3) value to 28 days post dose 3) in the S antibodies for each immunocompromised cohort (including the pooled immunocompromised cohort).
- Proportion of participants who have a post-treatment seroresponse ( $\geq 4$ -fold rise in titres from day of dosing visit 8 (pre-dose 3) value to 28 days post dose 3) as measured by SARS-CoV-2 neutralizing antibodies (pseudo-neutralization assay) for each immunocompromised cohort (including the pooled immunocompromised cohort).

The exploratory immunogenicity endpoints are:

- Post-treatment GMTs and GMFRs from day of dosing baseline value to 28 days post dose 3 in SARS-CoV-2 S antibodies in immunocompetent participants.
- Proportion of participants who have a post-treatment seroresponse ( $\geq 4$ -fold rise in titres from day of dosing baseline value to 28 days post dose 3) in the S antibodies in immunocompetent participants.

- Post-treatment GMTs and GMFRs from day of dosing baseline value to 28 days post dose 3 in SARS-CoV-2 neutralizing antibodies (pseudo-neutralization assay) in immunocompetent participants.

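### Capping titres at the ULoQ scores some unmeasurable dose-3 rises as non-responses when the reference is a post-vaccination titre

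*SAP*

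**What the plan says.** SAP section 16.1.5 fixes both ends of the assay range. Below the LLoQ, half the LLoQ is used; with an LLoQ of 30, "values of 15 (i.e., 30/2) are to be used in the summaries and analyses". Above the range: "Titre values measured as above upper limit of quantification (ULoQ) will be imputed at the ULoQ value".

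Section 16.1.1 defines the ratio: "The fold rise is calculated as the ratio of the post-vaccination titre level to the pre-vaccination titre level". Section 16.1.2 makes the outcome binary: "Seroresponse is a binary outcome where a success is when the fold rise in titres compared to baseline is" at least 4.

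The same 4-fold rule is used with a post-vaccination reference in three places:
- Section 16, supportive analysis, for S and for neutralizing antibodies in the immunocompromised cohorts: "rise in titres from day of dosing visit 8 (pre-dose 3) value to 28 days post dose 3".
- Table A, sensitivity estimand: "from visit 8 [pre-dose 3] to 28 days post third dose".
- Table A, the estimand comparing 28 days post dose 3 with 28 days post dose 2, which also covers immunocompetent participants: "rise in titres from 28 days post second dose to 28 days post third dose".

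The SAP has no not-evaluable category, no rule on diluting and re-assaying, and no count of participants at the ceiling. It states no ULoQ for either assay.

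**The concern.** One imputation rule serves two kinds of reference. Against a pre-first-dose baseline in SARS-CoV-2 naïve participants, the reference should be low and the cap leaves ample room for a 4-fold rise. Against a titre already raised by two doses, the room may be gone. The cap can then settle the answer before the post-dose-3 sample is read, and a result reported as above range becomes a definite non-response.

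These analyses ask what dose 3 adds to doses 1 and 2. The error runs in one direction, towards a smaller dose-3 effect, and falls on the participants with the highest titres after two doses. The planned output would give a single percentage, with nothing to show how many participants could not have been scored as responders.

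**Working it through.** **The SAP's own figure.** The only worked number in section 16.1.5 is 30/2 = 15, which reproduces. No ULoQ and no expected Visit 8-referenced rate is stated, so there is nothing further to reproduce.

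**Algebra, from sections 16.1.1, 16.1.2 and 16.1.5.** Let U be the ULoQ, R the reference titre and P the post-dose-3 titre.
- Computed rise = min(P, U) / min(R, U), which cannot exceed U / min(R, U).
- R = 0.20U: largest rise 5.0. R = 0.25U: 4.0, still a success. R = 0.30U: 3.33. R = 0.50U: 2.0. R at or above U: 1.0.
- So a response cannot be scored once R is strictly above U/4.

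With R above U/4 there are two cases. If P is at or below U, the true rise is below 4 and the non-response is correct. If P is above U, the true rise is unknown and is still scored as a non-response. The cap cannot create a responder: if R is at or below U/4, a capped P gives a rise of at least 4 and the true rise is larger; if R is above U/4, nobody is scored as responding.

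**Size, under assumptions that are not in the SAP.** Take the log2 Visit 8 titre as normal with SD 2 and the log2 rise as independent of it and normal with mean m and SD s. Let u = log2(ULoQ / Visit 8 GMT).
- P(R > U/4) = 1 − Φ((u − 2)/2): 0.3085 at u = 3 (8-fold), 0.1587 at u = 4 (16-fold), 0.0228 at u = 6 (64-fold), 0.0013 at u = 8 (256-fold).
- True rate = 1 − Φ((2 − m)/s): 0.500 for m = 2, s = 1.5; 0.159 for m = 1, s = 1.
- Loss = P(R > U/4) × true rate. Example at 8-fold: 0.3085 × 0.500 = 0.154, and 0.3085 × 0.159 = 0.049.
- Indeterminate share (R > U/4 and P > U) = the integral over x > u − 2 of the N(0, SD 2) density times P(log2 rise > u − x), evaluated numerically.
- Upper bound = scored rate + indeterminate share.

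| m, s | ULoQ / Visit 8 GMT | True rate % | Scored rate % | Loss, points | Indeterminate % | Upper bound % |
|---|---|---|---|---|---|---|
| 2, 1.5 | 8 | 50.0 | 34.6 | 15.4 | 23.3 | 57.9 |
| 2, 1.5 | 16 | 50.0 | 42.1 | 7.9 | 11.5 | 53.5 |
| 2, 1.5 | 64 | 50.0 | 48.9 | 1.1 | 1.5 | 50.4 |
| 2, 1.5 | 256 | 50.0 | 49.9 | 0.1 | 0.1 | 50.0 |
| 1, 1 | 8 | 15.9 | 11.0 | 4.9 | 17.0 | 28.0 |
| 1, 1 | 64 | 15.9 | 15.5 | 0.4 | 0.9 | 16.4 |

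A wider simulated sweep (SD of the log2 reference 1.5 to 2.5, geometric mean rise 2 to 4, SD of the log2 rise 1) gives losses of 4.0 to 17.2 points at 8-fold and 0.1 to 2.7 at 64-fold. No scenario produced a false responder.

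**The case against.** The algebra is not in dispute; its relevance to this trial is.

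- **Nothing shows that it occurs.** No ULoQ, GMT or SD is given, and how the laboratory handles above-range samples belongs to assay documents outside the SAP. This stands: the effect may be nil.
- **The larger figures come from chosen inputs.** A mean log2 rise of 2 puts the median participant exactly on the 4-fold threshold, and the 8-fold scenario then puts about a third of post-dose-3 titres above the ULoQ. This stands, and is why a range is given.
- **Reach is narrow.** The Visit 8 analysis is labelled supportive in section 16 and a sensitivity analysis in Table A. The Table A estimand from 28 days post dose 2 has no matching seroresponse endpoint in section 16. This stands.
- **The output may not be produced.** The addendum reports a sample well below plan, especially in the immunocompromised cohorts, pools those cohorts, and drops by-visit tables, between-arm comparisons and unspecified other outputs. The Visit 8 rate is not named as dropped, so its status is unclear.
- **Listings let a reader look.** Titres are listed individually, but section 16.1.5 promises as-reported values only below the LLoQ. This stands in part.
- **The cap is pre-specified and conservative, and no hypothesis is tested.** True, but a conservative single figure still does not disclose how much of it is a ceiling effect.

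A reader might infer three stronger things, none of which the SAP supports. First, that everyone with a Visit 8 titre above ULoQ/4 is misclassified: those with a later titre within range are correct non-responders, and some with an above-range titre truly rose less than 4-fold (in the first table row, 23.3 − 15.4 = 7.9 points). Second, that the primary or main dose-3 seroresponse endpoints are biased: they use the Day 1 baseline and are little affected. Third, that the rate is understated by 15 points: that is one assumed scenario.

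**Conclusion.** The point holds as a narrow gap in the rule. For seroresponse referenced to Visit 8 or to 28 days post dose 2, a participant with a reference titre above ULoQ/4 and a later titre above the ULoQ has an unknown rise and is recorded as a non-responder. The direction is certain: this cap can only lower the rate. The size is not determinable from the SAP. With a log2 Visit 8 SD of 2, a mean log2 rise of 1 to 2 and an SD of 1 to 1.5, the loss is about 5 to 15 points at an 8-fold margin and about 0.4 to 1 point at 64-fold; it is nil if no post-dose-3 titre exceeds the ULoQ. Given the supportive role of the main affected analysis and the doubt over whether it is still reported, this is a cheap improvement, not a flaw in the trial's main results.

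**What to change.** First state whether the Visit 8-referenced and post-dose-2-referenced seroresponse rates are still reported under the addendum. If they are, add to sections 16.1.2 and 16.1.5:

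- A participant whose reference titre exceeds ULoQ/4 and whose later titre is reported above the ULoQ is flagged as indeterminate for these rates.
- The planned rate, counting indeterminate participants as non-responders, is kept as the lower bound. Their number is shown, and one further row counts them as responders as the upper bound.
- Where the laboratory already reports a diluted end-point value, that value replaces the cap for these fold rises.

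The cost is a short SAP insertion and one table row plus a count; no new assay is required. If nobody is indeterminate, the count is zero and the rate is unchanged. Otherwise the reader gets a bounded rate in place of a single one, and the upper bound can overshoot the true rate (57.9% against 50.0% in the first table row), so it should be labelled as a bound and not as an estimate.

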#### **16.1.6. MODEL ADJUSTMENT**

The GMT endpoint will be analysed using an analysis of variance (ANOVA) model separately for each cohort (including the pooled immunocompromised cohort), and includes the log base 2-transformed value of titre as the dependent variable and visit, sex, and age group as fixed effects and participant as a random effect. On the log scale, the models will be used to estimate least square means for each cohort by visit. The model-adjusted titre levels will be derived as the LS means for each cohort and visit combination, plus the residual from the model fit. These values

will then be back-transformed.

All analysis detailed in [Section 16](#) will be repeated on model adjusted titre levels.

## 17. SAFETY ENDPOINTS

All safety summaries will be presented by cohort based on the SAF analysis set. There will be no statistical comparisons between the cohorts for safety data.

The secondary safety endpoints are:

- Reactogenicity: Incidence of local and systemic solicited AEs for 7 days after each dose of AZD1222 by eDiary.
- Incidence of unsolicited AEs for 28 days post dose after each vaccination.
- Incidence of Serious adverse events (SAEs), Medically attended adverse events (MAAEs) and AEs of special interest (AESIs) from Day 1 post treatment to last study visit.
- Absolute and change from baseline for safety laboratory measures

There are also other safety endpoints such as vital signs.

### 17.1. ADVERSE EVENTS

All AEs are considered to be unsolicited AEs (collected by 'open question' at study visits) unless categorized as solicited AEs recorded in an eDiary (see [Section 17.2](#)).

Non-serious AEs will be recorded for 28 days post each dose of study intervention. SAEs will be recorded from the time of signature of the informed consent form through the last participant contact. MAAEs and AESIs will be recorded from Day 1 through the last participant contact.

AEs will be coded using the MedDRA dictionary, version 23.0 or higher.

Overall summaries of number and percentage of participants, and number of events with following AE categories will be provided by cohort based on the SAF:

- All AEs

- All SAEs
- Related AEs by severity
- Related SAEs
- AEs leading to discontinuation from study intervention
- Related AEs leading to discontinuation from study intervention
- AEs leading to study discontinuation
- Related AEs leading to study discontinuation
- COVID-19 related AEs
- MAAEs
- AEs with outcome of death
- AESIs
- Related AESIs

Should a participant experience multiple events within a category, the participant will be counted only once for that category.

An overall summary of number and percentage of participants, and number of events within each of the categories described above will be provided for the period from 1-28 days post any dose by cohort based on the SAF.

Adverse events post the first study intervention occurring within 28 days of each dose will be summarized by SOC and PT by cohort, including exposure adjusted rates. Specific AEs will be counted once for each participant for calculating percentages. Exposure adjusted rate is calculated as number of participants with AEs in categories above/total patient-year exposure to investigational study intervention. Patient years is determined by summing the total number of follow-up days of each participant, and then dividing by 365.25. The exposure period is calculated from time of first intervention to end of study.

Summary of AEs occurring within 28 days post each intervention will be broken down further by post each dose, maximum severity and events related to study intervention. If the same AE occurs multiple times within a particular participant, the highest severity observed will be reported.

Non-serious AEs, including exposure adjusted rates, will be summarized by PT. AEs within 28 days of each study intervention will also be summarized by PT.

All AEs will be listed.

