#### 3.1. GENERAL DESCRIPTION

D8111C00010 is a Phase IV, open-label, non-randomized, multi-cohort, multicenter study of the immunogenicity and safety of AZD1222 for the prevention of COVID-19 in previously unvaccinated immunocompromised adults  $\geq 18$  years. Immunocompromised participants will receive primary vaccination with 3 IM doses of AZD1222 separated by 4 weeks and will continue to be followed to the end of the study. Immunocompetent participants will receive a primary vaccination series with 2 IM doses of AZD1222 separated by 4 weeks followed by a third dose booster 6 months after dose 1 and will continue to be followed to the end of the study.

The study includes adults  $\geq 18$  years with stable immunocompromising conditions or on stable doses of immunocompromising therapeutics, enrolled in 5 disease cohorts of approximately 60 participants each. A sixth cohort will contain approximately 60 immunocompetent participants. Participants will be allocated to the immunocompromised according to the underlying aetiology of their immunocompromised status.

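### The exposure-adjusted rate for adverse events within 28 days of a dose is divided by all follow-up to end of study, so it is diluted whenever follow-up runs past those windows

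*SAP*

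**What the plan says.** The relevant text is in one paragraph of SAP Section 17.1.

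- **Events counted:** "Adverse events post the first study intervention occurring within 28 days of each dose will be summarized by SOC and PT by cohort". The same sentence adds exposure-adjusted rates to this summary.
- **Rate:** "Exposure adjusted rate is calculated as number of participants with AEs in categories above/total patient-year exposure to investigational study intervention".
- **Person-time:** "Patient years is determined by summing the total number of follow-up days of each participant, and then dividing by 365.25".
- **Period:** "The exposure period is calculated from time of first intervention to end of study".

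No person-time restricted to the 28-day windows is defined anywhere in the SAP. Earlier in Section 17.1, non-serious events are said to be recorded only for 28 days after each dose, whereas SAEs, MAAEs and AESIs are recorded to the last contact. Section 17 lists the matching secondary endpoint as "Incidence of unsolicited AEs for 28 days post dose after each vaccination".

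The addendum, written after early termination, limits reporting to the final analysis and withdraws most adverse event outputs. It keeps the unsolicited AE summary by SOC and PT and refers to the main SAP for everything it does not change. It mentions neither the rate column nor the 28-day limit.

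**The concern.** A rate per patient-year is interpretable when the events in the numerator could have arisen at any point in the time counted below them. Here they could not. An event on a day outside every 28-day window is excluded from this table by definition, yet that day still counts as exposure.

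The rate therefore depends on how long participants stayed in the study after their windows closed. Two groups with the same risk after each dose would show different rates if one was followed longer, and the longer-followed group would look safer. Early termination makes unequal follow-up plausible. The two dosing schedules also place the third window at different times, so the dilution can differ between immunocompromised and immunocompetent participants who leave on the same day.

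**Working it through.** The SAP gives no numerical rate, so there is no figure to reproduce. The check compares the days in the SAP's denominator with the days on which an event could enter the table.

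**Inputs**

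- Immunocompromised schedule (Section 3.1): "Immunocompromised participants will receive primary vaccination with 3 IM doses of AZD1222 separated by 4 weeks". Doses on days 1, 29 and 57.
- Immunocompetent schedule (Section 3.1): two doses "separated by 4 weeks followed by a third dose booster 6 months after dose 1". Doses on days 1, 29 and 183, taking 6 months as the V1+182 visit.
- Last planned visit (Appendix 2, nominal visits): V1+364, that is 364 or 365 days depending on whether Day 1 is counted.
- Window: 28 days after each dose. The main count takes the dose day as Day 1 of the window. The alternative takes the dose day plus 28 further days, with shared days counted once.

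**Formula:** dilution factor = follow-up days ÷ days inside the union of the windows.

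**Planned design, all three doses received**

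| Window count | Window days | 364 ÷ days | 365 ÷ days |
|---|---|---|---|
| Dose day = Day 1, both groups | 84 | 4.33 | 4.35 |
| Dose day + 28, immunocompromised | 85 | 4.28 | 4.29 |
| Dose day + 28, immunocompetent | 86 | 4.23 | 4.24 |

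The factor is 4.23 to 4.35. The contributing share of follow-up is 84/365 = 23.0% to 86/364 = 23.6%.

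**Shorter follow-up.** Actual exit days and doses are not given, so the exit days below are assumptions. All doses scheduled by the exit day are taken as received, and the dose day is Day 1 of the window.

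| Group | Assumed exit day | Window days | Factor |
|---|---|---|---|
| Immunocompromised | 84 | 84 | 1.00 |
| Immunocompromised | 112 | 84 | 1.33 |
| Immunocompromised | 182 | 84 | 2.17 |
| Immunocompetent | 56 | 56 | 1.00 |
| Immunocompetent | 84 | 56 | 1.50 |
| Immunocompetent | 182 (before booster) | 56 | 3.25 |
| Immunocompetent | 210 (after booster window) | 84 | 2.50 |

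At exit on day 182 the two groups are diluted by different amounts, 2.17 and 3.25, because they have had three windows and two.

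**Fewer doses.** The factors above are not upper bounds. A participant followed to day 365 after two doses has 56 to 57 window days, giving 365/57 = 6.4 to 365/56 = 6.5. After one dose there are 28 to 29 window days, giving 365/29 = 12.6 to 365/28 = 13.0.

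**Illustration.** Assume 20 of 60 participants have a given event inside the windows and all are followed to day 365.

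- SAP rule: 20 ÷ (60 × 365/365.25) = 0.33 per patient-year.
- Window person-time, 84 days each: 20 ÷ (60 × 84/365.25) = 1.45 per patient-year.

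The percentage, 20/60 = 33.3%, is the same under both.

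**The case against.** The strongest reply concerns reach. The addendum now governs what is reported, and it says nothing of a 28-day limit or a rate column for the SOC/PT table it keeps. Section 17.1 treats every event not solicited in the eDiary as unsolicited, which includes SAEs, MAAEs and AESIs recorded to last contact. If the table covers all of these, some events outside the windows do reach the numerator. This stands as an uncertainty about the final output. It does not rescue the main SAP wording, and even in an unrestricted table the mismatch would remain for non-serious events that are none of these, because they are collected only in the windows.

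Second, first dose to end of study is an openly stated convention, and it suits the SAE, MAAE and AESI tables. That is true, but the addendum withdraws those tables, and stating the denominator does not make it fit a numerator limited to 28 days.

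Third, the four-fold figure assumes three doses and a full year, which early termination has overtaken. This stands: the figure describes the planned design only.

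Fourth, the consequences are small. Section 17 says "There will be no statistical comparisons between the cohorts for safety data", no hypothesis is tested, and the addendum itself concedes limited interpretability. This also stands, and it sets the rating.

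Finally, window person-time would still not be censored at the first event although participants are counted once. That limit is already present in the SAP's own formula. Window person-time removes the mismatch raised here, but not that limit.

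**Conclusion.** The concern holds, as a minor point. Followed as written, Section 17.1 divides events from the 28-day windows by person-time that includes days on which no event can count.

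- **Size on the planned schedule:** 4.2 to 4.35 times too low relative to time in the windows, assuming three doses and follow-up to V1+364.
- **Size in the terminated study:** unknown. It could be about 1.0 if participants left as their windows closed. It would be larger with longer follow-up after the last window, or with fewer doses at the same follow-up.
- **Reach:** one descriptive column in one table. The natural reading of the addendum is that the column survives, but the addendum does not say so.
- **Not affected:** the counts and percentages, which report the secondary endpoint. The non-serious AE table by PT has the same fault in the main SAP but is withdrawn, as are the SAE, MAAE and AESI tables, so nothing is asked for any of these.

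**What to change.** State in the addendum whether the SOC/PT table that is kept is limited to events within 28 days of a dose. If it is, also state which of these applies:

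- **(a)** Use person-time inside the 28-day windows, with each window truncated at the next dose, withdrawal, death or study end, and name this denominator in a footnote.
- **(b)** Drop the rate column and report counts and percentages only.

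Either takes one or two lines in the addendum. Option (a) needs minor programming; its rates will look less favourable and depend on the footnote to be read correctly. Option (b) needs almost no programming and loses only the column. It also avoids the question of censoring at first event.
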